6.2.5. Study Exposure

Study duration, defined as time on study from the injection to study discontinuation, study completion, last contact date, or data cutoff date, whichever occurs earlier, will be summarized based on Safety Set.

6.2.6. Major Protocol Deviations

Major protocol deviations are a subset of protocol deviations that may significantly impact the completeness, accuracy, or reliability of the study data or that may significantly affect a participant's rights, safety, or well-being. Major protocol deviations rules will be developed and finalized before database lock.

The number and percentage of the participants with each major protocol deviation type will be provided by treatment group as defined in [Section 6.1](#) based on the Randomized Set.

Major protocol deviations will be presented in a listing.

Selected major protocol deviations deemed to impact critical data will lead to exclusion from the PPSI or PPSE.

6.3. Safety Analysis

Following section is applicable for both Part 1 and Part 2:

Safety and reactogenicity will be assessed by clinical review of all relevant parameters including SARs (local and systemic), unsolicited AEs, treatment-related AEs, severe AEs, SAEs, MAAEs, AESIs, and AEs leading to withdrawal from study participation, vital signs, and physical examinations findings. Unsolicited AEs will be coded by SOC and PT according to the MedDRA. The Toxicity Grading Scale for Healthy Adult and Adolescent Volunteers Enrolled in Preventative Vaccine Clinical Trials ([DHHS 2007](#)) is used in this study for SARs.

Safety analyses will be based on the Safety Set. The Solicited Safety Set will be used for analyses of SARs.

6.3.1. Adverse Events

A treatment-emergent AE (TEAE) is defined as any event occurring during the study that was not present before exposure to study vaccine, or any event already present that worsens after exposure to study vaccine. Worsening of a pre-existing condition after vaccination will be reported as a new AE.

Adverse events will also be evaluated by the investigator for the coexistence of MAAE which is defined as an AE that leads to an unscheduled visit to a healthcare practitioner.

Refer to Protocol Appendix 3 for the definitions of AEs of special interest (AESI).

Analyses of unsolicited AEs will be summarized by stage, up to 28 days after vaccination and throughout the study and by treatment group ([Section 6.1](#)).

All summary tables (except for the overall summary of AEs) for unsolicited AEs will be presented by SOC and PT for TEAEs with counts of participants included. When summarizing the number and percentage of participants with an event, participants with multiple occurrences of the same AE or a continuing AE will be counted once. Participants will be presented according to the highest severity (the strongest causality) in the summaries by severity (of related AEs), if participants reported multiple events under the same SOC and/or PT.

Percentages will be based upon the number of participants in the Safety Set.

6.3.1.1. Incidence of Adverse Events

An overall summary of unsolicited TEAEs including the number and percentage of participants by treatment group who experience the following will be presented:

- Any unsolicited TEAEs
- Any serious TEAEs
- Any fatal TEAEs
- Any unsolicited treatment-emergent AESIs
- Any unsolicited TEAEs that are medically-attended (MAAEs)
- Any unsolicited TEAEs leading to discontinuation from participation in the study
- Any unsolicited severe TEAEs
- Any unsolicited non-serious TEAEs
- Any unsolicited severe non-serious TEAEs

The table will also include number and percentage of participants with unsolicited TEAEs that are treatment-related in each of the above categories.

In addition, separate listings containing individual participant data for AEs leading to death, SAEs, AESIs, and a listing of AEs prior to death in the subset of deceased participants will be provided separately.

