Hypersensitivity AEs were reported in 1.5% of vaccine recipients and 1.1% of placebo recipients. Hypersensitivity events in the vaccine group included injection site rash and injection site urticaria, which are likely related to vaccination. There have been no cases of severe hypersensitivity or anaphylactic reactions reported immediately after vaccination in the trial to date.

There were 3 reports of Bell's palsy in the mRNA-1273 vaccine group (one of which was a serious AE [SAE]), which occurred 22, 28, and 32 days after vaccination, and 1 in the placebo group which occurred 17 days after vaccination. Currently available information on Bell's palsy is insufficient to determine a causal relationship with the vaccine.

SAEs were reported at the same rates in participants who received mRNA-1273 and placebo from the first dose until the last observation. There were 2 SAEs of facial swelling in vaccine recipients with a history of injection of dermatological fillers. The onset of swelling was reported 1 and 2 days, respectively, after vaccination and was likely related to vaccination. There was 1 SAE of intractable nausea and vomiting in a participant with prior history of severe headache and nausea requiring hospitalization. This event occurred 1 day after vaccination and was likely related to vaccination.

There were no other notable patterns or numerical imbalances between study arms for specific categories of AEs (including other neurologic, neuro-inflammatory, and thrombotic events) that would suggest a causal relationship to mRNA-1273.

In the post-authorization period, there have been very rare reports of anaphylaxis following mRNA-1273 administration. In addition, there have been very rare reports of myocarditis and pericarditis occurring after vaccination with COVID-19 mRNA vaccines. The majority of the cases have been reported in young males shortly after the second dose of the vaccine. These are typically mild cases and individuals tend to recover within a short time following standard treatment and rest. Investigators and study participants should be alert to the signs and symptoms of myocarditis and pericarditis. Safety will be monitored throughout the study.

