7. DELAY OR DISCONTINUATION OF STUDY INTERVENTION AND PARTICIPANT DISCONTINUATION/WITHDRAWAL

7.1. Participant Discontinuation/Withdrawal from the Study

Participants who withdraw or are withdrawn from the study will not be replaced.

From an analysis perspective, a “withdrawal” from the study refers to a situation wherein a participant does not return for the final visit planned in the protocol.

Participants can withdraw consent and withdraw from the study at any time, for any reason, without prejudice to further treatment the participant may need to receive. The investigator will request that the participant complete all study procedures pending at the time of withdrawal.

If a participant desires to withdraw from the study because of an AE, the investigator will attempt to obtain agreement to follow-up with the participant until the event is considered resolved or stable and will then complete the end of study eCRF.

All data collected until the date of withdrawal or last contact of the participant will be used for the analysis.

Information related to the withdrawal will be documented in the eCRF. The investigator will document whether the decision to withdraw a participant from the study was made by the participant or by the investigator, as well as which of the following possible reasons was responsible for withdrawal:

- AE (specify)
- SAE (specify)
- Solicited AR or reactogenicity event (specify)
- Death
- Lost to follow-up (LTFU)
- Physician decision (specify)
- Pregnancy
- Protocol deviation
- Study terminated by Sponsor
- Withdrawal of consent by participant (specify)
- Other (specify)

Participants who are withdrawn from the study because of AEs (including SAEs, solicited ARs, or reactogenicity events) must be clearly distinguished from participants who are withdrawn for other reasons. Investigators will follow-up with participants who are withdrawn from the study as result of an AE, SAE, solicited AR, or reactogenicity event until resolution of the event.

A participant withdrawing from the study may request destruction of any samples taken and not tested, and the investigator must document this in the site study records.

If the participant withdraws consent for disclosure of future information, the Sponsor may retain and continue to use any data collected before such a withdrawal of consent (see [Section 11.1.6](#)).

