Headache	None	No interference with activity	Repeated use of over-the-counter pain reliever > 24 hours or some interference with activity	Significant; any use of prescription pain reliever or prevents daily activity	Requires emergency room visit or hospitalization
Fatigue	None	No interference with activity	Some interference with activity	Significant; prevents daily activity	Requires emergency room visit or hospitalization
Myalgia (muscle aches all over body)	None	No interference with activity	Some interference with activity	Significant; prevents daily	Requires emergency room visit or

				activity	hospitalization
Arthralgia (joint aches in several joints)	None	No interference with activity	Some interference with activity	Significant; prevents daily activity	Requires emergency room visit or hospitalization
Nausea/vomiting	None	No interference with activity or 1-2 episodes/24 hours	Some interference with activity or > 2 episodes/24 hours	Prevents daily activity, requires outpatient intravenous hydration	Requires emergency room visit or hospitalization for hypotensive shock
Chills	None	No interference with activity	Some interference with activity not requiring medical intervention	Prevents daily activity and requires medical intervention	Requires emergency room visit or hospitalization
Fever (oral)	< 38.0°C < 100.4°F	38.0-38.4°C 100.4-101.1°F	38.5-38.9°C 101.2-102.0°F	39.0-40.0°C 102.1-104.0°F	> 40.0°C > 104.0°F

¹. Grading of Grade 4 events will be determined per investigator and assessment is recorded on the reactogenicity event page in the electronic case report form.

Any solicited AR that meets any of the following criteria must be entered into the participant's source document and must also be recorded in the participant's eCRF:

- Solicited local or systemic AR that results in a visit to a healthcare practitioner (HCP; MAAE)
- Solicited local or systemic AR leading to the participant withdrawing from the study or the participant being withdrawn from the study by the investigator (AE leading to withdrawal)
- Solicited local or systemic AR continuing beyond 7 days post injection
- Solicited local or systemic AR that leads to participant withdrawal from IP
- Solicited local or systemic AR that otherwise meets the definition of an SAE

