9.6.3. Safety Analyses

All safety analyses will be based on the Safety Set, except analyses of solicited ARs, which will be based on the Solicited Safety Set.

Safety and reactogenicity will be assessed by clinical review of all relevant parameters including solicited ARs (local and systemic ARs), unsolicited AEs, and physical examination findings.

The number and percentage of participants with any solicited local AR, with any solicited systemic AR, with any solicited AR during the 7-day follow-up period after vaccination, and with Grade 3 or higher solicited AR will be provided. A 2-sided 95% exact CI using the Clopper Pearson method will be provided for the percentage of participants with any solicited AR.

The number and percentage of participants with unsolicited AEs, treatment-related AEs, severe AEs, SAEs, MAAEs, AESIs, and AEs leading to withdrawal will be summarized. The follow-up windows for AEs are detailed in the SoE ([Table 1](#) and [Table 2](#)). Unsolicited AEs will be presented

by MedDRA system organ class and preferred term. Unsolicited AEs will be coded according to the MedDRA Dictionary for Adverse Reaction Terminology.

Pregnancy outcomes will also be summarized.

[Table 12](#) summarizes the analysis strategy for safety parameters. Further details will be described in the SAP.

Table 12: Analysis Strategy for Safety Parameters

Safety Endpoint	Number and Percentage of Participants, Number of Events	95% CI
Any solicited AR (overall and by local, systemic)	X	X
Any unsolicited AE	X	—
Any SAE	X	—
Any AESI	X	—
Any unsolicited MAAE	X	—
Any unsolicited treatment-related AE	X	—
Any treatment-related SAE	X	—
Discontinuation due to AE	X	—
Any severe AE	X	—
Any treatment-related severe AE	X	—

Abbreviations: AE = adverse event; AESI = adverse event of special interest; AR = adverse reaction; CI = confidence interval; MAAE = medically attended adverse event; PT = preferred term; SAE = serious adverse event; SOC = system organ class.

Notes: 95% CI using the Clopper-Pearson method, X = results will be provided. Unsolicited AEs will be summarized by SOC and PT coded by MedDRA.

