3.1.2. Primary Safety Endpoints

The primary safety objectives will be evaluated by the following endpoints in Part 1 and Part 2:

- Solicited local and systemic reactogenicity adverse reactions (ARs) during a 7-day follow-up period after vaccination.
- Unsolicited adverse events (AEs) through the 28-day follow-up period after vaccination.

- Serious AEs (SAEs), medically attended AEs (MAAEs), AEs leading to withdrawal, and AEs of special interest (AESIs) from Day 1 to end of study.

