6.2. Background Characteristics

6.2.1. Disposition

The number and percentage of participants in the following categories (analysis sets defined in [Section 5](#)) will be summarized by treatment group as defined in [Section 6.1](#):

- FAS
- mITT
- PPSI
- PPSI-Neg
- Solicited Safety Set
- Safety Set

- PPSE

The denominators of the percentages will be based on participants in the Full Analysis Set. The number of participants in the following categories will be summarized based on participants screened:

- Number of participants screened
- Number and percentage of screen failure participants and the reason for screen failure

The percentage of participants who screen failed will be based on the number of participants screened. The reason for screen failure will be based on the number of participants who screen failed.

For Solicited Safety Set, the percentage will be based on the number of participants in the treatment group within the Safety Set (as treated).

Summary of reasons for participants excluded from PP Sets will also be provided.

The number and percentage of participants in each of the following disposition categories will be summarized based on the Randomization Set:

- Received IP
- Completed study

This study treatment only consists of a one-dose booster, thus discontinuation from study treatment is not applicable in this study.

In addition, a listing of participant deaths will be provided separately.

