6.3.1.2. TEAEs by System Organ Class and Preferred Term

Summary tables of TEAEs by SOC and PT up to 28 days, and throughout the study after the IP administration by using frequency counts and percentages of participants with an event will be provided for:

- All unsolicited TEAEs*
- All serious TEAEs*
- All unsolicited treatment-emergent AESIs*
- All unsolicited severe TEAEs*
- All unsolicited TEAEs that are medically-attended*
- All unsolicited TEAEs leading to discontinuation from participation in the study

* Tables will also be presented for treatment-related TEAEs up to 28 days after IP administration.

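### The SAP's discontinuation and MAAE counts leave out solicited reactions that led to withdrawal or a healthcare visit, although the protocol places such reactions in those categories

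*SAP*

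**What the plan says.** - **Endpoint.** SAP 3.1.2 lists among the primary safety endpoints: "Serious AEs (SAEs), medically attended AEs (MAAEs), AEs leading to withdrawal, and AEs of special interest (AESIs) from Day 1 to end of study". Nothing there limits MAAEs or withdrawals to unsolicited events. Protocol Tables 3 and 4 agree.
- **Classification.** Protocol 8.10.3 lists solicited ARs that must be entered in the source document and the eCRF. One entry is "Solicited local or systemic AR that results in a visit to a healthcare practitioner (HCP; MAAE"; the next is a solicited AR leading to withdrawal from the study, labelled as an AE leading to withdrawal.
- **Withdrawal reasons.** Protocol 7.1 gives "Solicited AR or reactogenicity event (specify" as a reason separate from AE and SAE. It also requires that participants withdrawn because of AEs, solicited ARs included, be clearly distinguished from other withdrawals.
- **Protocol analysis table.** Table 12 in protocol 9.6.3 has a row "Discontinuation due to AE" with no limit to unsolicited events. Its MAAE row is limited to unsolicited MAAEs.
- **SAP tables.** SAP 6.3.1.1 has "Any unsolicited TEAEs leading to discontinuation from participation in the study" and a medically attended row with the same limit. SAP 6.3.1.2 repeats both limits by SOC and PT.
- **Declared changes.** SAP Section 7 records none. SAP Section 1 says that the SAP governs where its methods differ from the protocol's.

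**The concern.** Two components of the primary safety endpoint are defined without regard to whether the event was solicited, but are tabulated for unsolicited events only. The events left out are informative. Protocol 8.10.3 treats every solicited AR as causally related to dosing, so these are withdrawals and healthcare visits attributed to the vaccine, in a trial that compares vaccines. If one vaccine caused more withdrawals or visits through early reactogenicity, the planned discontinuation and MAAE rows would not show it. Because the SAP prevails over the protocol, the narrower discontinuation count is the one that would be produced.

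**Working it through.** No figure in the plan depends on this point, so there is none to reproduce. The check is whether any planned output recovers the event.

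**Step 1: trace one event.** Take a non-serious solicited AR that starts within 7 days of injection and leads to withdrawal or a healthcare visit.

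- SAP 6.3.1.1 and 6.3.1.2, discontinuation and MAAE rows: excluded, because the event is solicited.
- Serious and fatal rows: not applicable, because the event is non-serious.
- SAP 6.3.2, solicited AR summaries: the reaction is counted by grade, reporting day, onset day, duration and persistence. None of these shows withdrawal or a healthcare visit as such.
- SAP 6.2.1, disposition: "The number and percentage of participants in each of the following disposition categories will be summarized based on the Randomization Set". The categories are receipt of IP and study completion, with no reasons for withdrawal.
- SAP 6.3.1.1, listings: deaths, SAEs, AESIs, and AEs preceding death. There is none for MAAEs or withdrawals.
- SAP 6.5.4, listing of solicited ARs: only for participants infected with SARS-CoV-2.

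The reaction appears as a reaction, but its consequence is identified nowhere.

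**Step 2: locate the conflict for each category.**

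| Category | Endpoint and protocol 8.10.3 | Protocol Table 12 | SAP 6.3.1.1 | Where the conflict lies |
|---|---|---|---|---|
| Leading to withdrawal | includes solicited ARs | no limit | unsolicited only | SAP against protocol, undeclared |
| MAAE | includes solicited ARs | unsolicited only | unsolicited only | inside the protocol |

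**Step 3: scale, for illustration only.** Let q be the assumed share of participants whose only event in the category is a non-serious solicited AR starting within 7 days. The documents give no value for q. With n participants per arm, the expected number left out is n × q, and the chance that at least one is left out is 1 − (1 − q)^n. Planned arm sizes are 1462 in Part 2 and 300 to 500 in Part 1.

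| q (assumed) | Part 2, n = 1462 | Part 1, n = 300 | Part 1, n = 500 |
|---|---|---|---|
| 0.05% | 0.7 (52%) | 0.15 (14%) | 0.25 (22%) |
| 0.1% | 1.5 (77%) | 0.3 (26%) | 0.5 (39%) |
| 0.5% | 7.3 (99.9%) | 1.5 (78%) | 2.5 (92%) |
| 1% | 14.6 (about 100%) | 3.0 (95%) | 5.0 (99%) |

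Example: 1462 × 0.001 = 1.46, and 1 − 0.999^1462 = 0.768.

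**The case against.** **On MAAEs, the SAP follows the protocol.** Table 12 plans unsolicited MAAEs only, and protocol 8.10.4 has investigators look for MAAEs among unsolicited AEs. This stands: it is no SAP departure. It does not settle the matter, because 8.10.3, the endpoint and the text of 9.6.3 carry no such limit.

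**The row label is honest.** A row headed as unsolicited makes no claim about solicited reactions, so a zero there would not be false. That is fair, but the endpoint is broader than the row, and no other output supplies the remainder.

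A reader might also infer more than the documents support:

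- *That every such solicited AR is lost.* Solicited terms starting after the 7-day period are unsolicited by definition (protocol 8.10.1) and can reach these rows. Serious ones fit the serious rows as labelled, although the lead-in to SAP 6.3.1.1 speaks of unsolicited TEAEs. Reactions reported verbally have unclear routing: protocol 8.9.4 calls them unsolicited but sends them to the solicited section of the eCRF. Table 8 also builds medical care into several Grade 3 and most Grade 4 definitions, and those grades are tabulated, so part of the information survives.
- *That severe events are lost.* SAP 6.3.2 tabulates solicited ARs of Grade 3 or higher. Only a combined count is absent, and it would mix Table 8 grading with the investigator-judged severity scale of protocol 8.10.8.
- *That AESIs are lost.* No solicited term in Table 8 is itself an AESI concept in Table 13, and the AESI listing is not limited to unsolicited events.
- *That late related events disappear.* SAP 6.3.1.2 says "Tables will also be presented for treatment-related TEAEs up to 28 days after IP administration", and the Bell's palsy cases in protocol 2.3.2, "which occurred 22, 28, and 32 days after vaccination", might suggest a gap. They come from another trial, and the protocol calls the causal information insufficient. Bell's palsy is an AESI here, and AESIs are tabulated throughout the study and listed. Only the related-event breakdown by SOC and PT stops at 28 days.

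**Conclusion.** The point holds for two categories and one kind of event: non-serious solicited ARs that start within 7 days and lead to withdrawal or a healthcare visit. As written, the SAP does not count them in the corresponding primary safety component. For discontinuation this is an undeclared narrowing of protocol Table 12. For MAAEs it is an unresolved conflict within the protocol that the SAP inherits. Whether the reported figures would change depends on such events occurring. The number is unknown, and the values of q above are assumptions. The documents do not support extending the finding to severe events, AESIs or late-onset related events, or describing the loss of solicited events as total. The change should be made because the affected counts belong to a primary endpoint and the repair is small.

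**What to change.** 1. In SAP 6.3.1.1, keep the unsolicited rows and add beside them two rows that include solicited ARs: one for any AE leading to discontinuation and one for any MAAE. Alternatively, add a table to SAP 6.3.2 of solicited ARs that were medically attended or led to withdrawal.
2. In SAP 6.2.1, add reasons for withdrawal, with the solicited-reaction reason from protocol 7.1 on its own line.
3. Align protocol Table 12 with protocol 8.10.3 on MAAEs, so that the definition and the planned summary agree.
4. Record in SAP Section 7 any remaining difference from Table 12.

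The cost is a few table rows and some wording. Protocol 7.1 already requires the withdrawal reason in the eCRF, and protocol 8.10.3 requires the qualifying solicited ARs to be recorded there. The eCRF itself is not among the documents, so the sponsor should confirm that it flags a healthcare visit on the solicited AR record.
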